## 4. Study design

### 4.1 Design overview

Study NKF-INS(A)-101 is a Phase 1, 12-hour euglycemic glucose clamp study conducted using a randomized, double-blind, three-period, three-treatment, six-sequence crossover design. The study will compare single doses of the proposed insulin biosimilar (NKF-INS(A)) with respective EU- and US- reference products in healthy male participants.

Written informed consent will be obtained from all participants, and the study will be conducted in accordance with the principles of Good Clinical Practice (GCP) as defined by the International Conference of Harmonization (ICH).

The study will comprise:

- A screening period of up to 4 weeks (Days -28 to -1) to obtain informed consent and assess eligibility for participation,

---

- Three treatment periods each consisting of 1-day dose administrations and euglycemic clamp periods (periods 1, 2, and 3) separated by a washout period of 3-14 calendar days between treatment periods 1 and 2, and a washout period of 5-21 calendar days between treatment periods 2 and 3, and
- A follow up period of 2-11 days after last dose.

The entire study duration will be a maximum of 11 weeks. Procedures listed for the post-study visit will be performed in the event of early withdrawal from the study.

Three insulin products (NKF-INS(A), EU-Novorapid®, and US-Novolog®) will be administered over three treatment periods. Upon admission to the clinical research unit (CRU) on Day -1, participants will be randomized to one of six treatment sequences in a 1:1:1:1:1:1 ratio, receiving a single subcutaneous (SC) dose of 0.3 U/kg administration of one of the three study drugs on each dosing day.

A 12-hour euglycemic glucose clamp will be conducted using a manual clamp technique, which will monitor the participant's blood glucose and administer glucose infusion rate (GIR) to maintain blood glucose close to the target blood glucose concentration. The clamp procedure will be initiated, maintained, and terminated, in accordance with the site standard operating procedures (SOPs). The participant's blood glucose will be maintained within a pre-defined target window per site SOP and clinical judgement for the participant by manually adjusting the GIR.

Blood samples will be collected at pre-specified intervals before and up to 12 hours after dosing for measurement of blood glucose, serum insulin, and C-peptide.

[figure not shown]
#### 4.1.1 Sample Size Considerations

A literature review of similar studies was conducted in order to inform the assumptions for the sample size, for the primary endpoints of  $AUC_{0-\infty}$  and  $C_{max}$  (see Table 9 in the NKF-INS(A)-101 CSP; Version 2.0, 6-May-2024).

The CV value ranged from 23.8% to 30.8%, with a mean value of 25.4%. The CV of the Innovator study was 25.3%. Based on the above data, the CV value is selected as 26%.

The sample size was calculated using PASS software [2] with following parameters including 90% power, dropout rate 20%,  $\alpha=0.05$ , 90% confidence interval (CI), assumed actual ratio 0.95 within 80-125%,  $N=40$ ; taking account of 20% dropout, the sample size is determined as  $N=54$  to have at least 36 evaluable participants.

Figure 4.1: Study Design Schematic (from Protocol v2.0, 06-May-2024)

Abbreviations: EU = European Union; US = United States

## 4.2 Schedule of events

Please refer to Table 3 in the CSP for NKF-INS(A)-101 v2.0 06-May-2024.

Table 4.2: Pharmacokinetic, pharmacodynamic, C-peptide and glucose sampling schedule (from Protocol v2.0, 06-May-2024).

Sample	Pre-dose (minutes)		Post-dose (minutes)																			
	60	30	0	5	10	20	30	40	50	60	75	90	105	120	135	150	180	210	240	300	600	720 (12 hours)
Insulin (serum)	X	X	X	X	X	X	X	X	X	X	X	X	X	X	X	X	X	X	X	X	X	X
C-peptide (serum)	X	X	X	X	X	X	X	X	X	X	X	X	X	X	X	X	X	X	X	X	X	X
Blood glucose				Every 3 minutes										Every 5 minutes					Every 10 minutes			

## 5. Analysis populations

Agreement and authorization of participants included/excluded from each analysis population will be reached prior to final database hard lock. The Sponsor will supply a list of all participants to be excluded from the relevant analysis populations, including the reason(s) for exclusion from the analysis populations.

All protocol deviations (major or minor) that occur during the study will be considered for their severity/impact in terms of adversely influencing the integrity or reliability of results and may be taken into consideration when participants are assigned to analysis populations. All analysis exclusions will be clearly documented with reasons for exclusion.

### 5.1 Screening Analysis Set

This analysis population will include all participants who provided written informed consent, and provided demographic and/or baseline screening assessments, regardless of the participant's randomization status. Screening failures will be included in this analysis population.

**5.2 Enrolled Analysis Set/ Full Analysis Set (FAS)**

This analysis population includes all individuals who signed the ICF.

**5.3 Safety Analysis Set (SAF)**

This analysis population will include all participants who received any amount of study treatment. Analyses based on the SAF population will reflect the actual IP administered to participants, regardless of the randomization list. This population will be used for the analysis of safety.

**5.4 Pharmacokinetic Concentration Analysis Set (PKCS)**

The PK Concentration population will include all participants in the SAF who received any amount of study treatment and have at least 1 post-baseline reportable PK result.

**5.5 Pharmacokinetic Parameter Analysis Set (PKPS)**

The PK Parameter Population will include all participants in the PKC who have at least 1 PK parameter derived.

**5.6 Pharmacodynamic Parameter Analysis Set (PDS)**

The PD Parameter Population will include all participants in the SAF who have at least 1 PD parameter derived.

**6. General considerations****6.1 Visit and date conventions**

Visit day will be calculated from the reference start date which will be used to present start/stop day of assessments and events. The *reference start date* is defined as the date of first IP administration. The following conventions will be used for visit references:

- *Visit day* = *date of event* – *reference start date* + 1
- *Visit week* =  $\frac{\text{visit day}}{7}$ , rounding up to next whole number
- *Visit month* =  $\frac{\text{visit day}}{30.44}$ , rounding up to next whole number

No visit windowing (i.e. remapping of visits based on visit windows) will be performed for this study. The assigned nominal visit will be used for by-visit summaries. In the situation where the assessment/event date is partial or missing, visit day/week/month, and any corresponding durations will appear missing in the data listings. Unscheduled measurements will not be included in by-visit summaries. In the case of a retest (same visit number assigned), the last available measurement for that visit will be presented for by-visit summaries. Data listings will include scheduled, unscheduled, retest and early discontinuation data. Study visit will be assigned as delineated in Table 6.1:

	Screen	Euglycemic Clamp Procedure Treatment Periods 1-3				Post-Study Visit
		Admission		Clamp Procedure	Post Clamp	
Visit Day	-28 to -1	Period 1	-1	1	2	16 - 52
		Period 2	5 - 16	6 - 17	7 - 18	
		Period 3	12 - 39	13 - 40	14 - 41	
Visit No.	1	Period 1	2	3	3	8
		Period 2	4	5	5	
		Period 3	6	7	7	

*Washout periods vary between treatment periods: washout period of 3-14 calendar days between treatment period 1 and 2, and a washout period of 5-21 calendar days between treatment periods 2 and 3.*

## 6.2 Baseline

Unless stated otherwise, baseline is defined as the last non-missing observation made prior to the first administration of IP.

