9 Supine systolic and diastolic blood pressure, pulse, and respiratory rate will be recorded at screening, before administration of the study drug, at the end of the clamp (before discharge from the study center) and at the EOS visit. Body temperature (temporal or ear) will be recorded at screening and before administration of study drug (either standing or supine). All vital signs will be measured after the participant has been resting in a supine position for at least 5 minutes.

10 Hematology (ethylenediaminetetraacetic acid tubes): full and differential blood count, WBC count, RBC count, Hb, HCT, MCV, MCH, MCH concentration, absolute differential count (neutrophils, lymphocytes, monocytes, eosinophils and basophils), and platelets.

11 Clinical chemistry (serum separator tubes): potassium, sodium, urea, chloride, phosphorus, creatinine, calcium, albumin, total and direct bilirubin, creatine kinase, ALP, GGT, AST, ALT, lactate dehydrogenase, total cholesterol, triglycerides, and glucose.

12 Blood coagulation tests (citrated tubes): PT, aPTT, and INR.

13 Tests for HIV, HBsAg, IgM anti-HBc, and HCV, performed using commercially available test kits. Pre- and post-test counseling will be provided as appropriate.

14 Urinalysis (dipstick): appearance, bilirubin, glucose, ketone, specific gravity, blood, pH, protein, urobilinogen, nitrite, leucocytes. Abnormal urinalysis results may be repeated at the discretion of the Investigator.

15 A rapid, one-step screening test for simultaneous, qualitative detection of multiple drugs and drug metabolites will be used. Subjects with alleged false positive test results will be excluded from the study. However, a positive test may be repeated once at the discretion of the Investigator.

16 Alcohol breath test using a portable breath alcohol measuring device. The test will be performed at screening, at admission to each treatment period and at random. If any of these tests are positive, the subject will not be allowed further participation in the study.

17 Oral glucose tolerance test may be completed after all other eligibility has been determined. For participants who re-screen, oral glucose tolerance test does not need to be repeated if completed within the last 6 months.

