## 6.4 Common calculations

For quantitative measurements, change from baseline will be calculated as: (Test value at Visit Day X – Baseline value), where the baseline value is defined as the last non-missing observation taken prior to first exposure to IP.

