### 20.1 Variables and derivations

For vital signs, baseline is defined as the last observation made prior to the first administration of IP.

---

The following vital signs will be reported for this study:

- Systolic blood pressure (mmHg)
- Diastolic blood pressure (mmHg)
- Heart rate (bpm)
- Body temperature (°C) (temporal or ear temperature measurements).
- Respiratory rate (breaths/min)

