### 23.2 Pharmacodynamic parameters

The PD similarity will be assessed using the parameters provided in Table 23.2 and by assessing:

- Time from study drug administration until the blood glucose concentration has decreased by at least 5mg/dL from baseline (onset of action).
- The difference between tGIR, 50%-late and the onset of action (duration of action).
- Total amount of glucose infused during clamp procedure (Gtot).

*Table 23.2: PD Parameters and their descriptions.*

PD Parameter	Description
AUCGIR 0-12h	Area under the GIR-time curve from 0 to 12 hours
GIR max	The maximum GIR of glucose
AUCGIR 0-4h	Area under the GIR-time curve from 0 to 4 hours
AUCGIR 0-6h	Area under the GIR-time curve from 0 to 6 hours
AUCGIR 6-last	Area under the GIR-time curve from 6 hours until the end of clamp
AUCGIR 0-t	Area under the GIR-time curve from 0 hours to the last quantifiable concentration time
AUCGIR 0-∞	Area under the GIR-time curve from 0 hours to the last quantifiable concentration time with extrapolation to infinity
AUCGIR 0-end of clamp	Area under the GIR-time curve from 0 hours to end of clamp
T max.GIR	Time to maximum GIR
tGIR,50%-early	Time to half-maximum GIR before GIR max
tGIR,50%-late	Time to half-maximum GIR after GIR max (indicator of end of duration of action)

Estimates of PD parameters will be listed and summarized (N, arithmetic and geometric mean, SD, CV%, median, minimum and maximum) by treatment, descriptively and graphically.

Endogenous insulin suppression via C-peptide measurements will also be explored. These values include corrected and uncorrected C-peptide concentrations. C-peptide corrected estimates of exogenous insulin will be calculated using Owen's method [5].

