## 24. Euglycemic Clamp Procedure and Performance

NKF-INS(A), US-NovoLog®, and EU-NovoRapid® will be administered using a euglycemic glucose clamp at targeted blood glucose concentrations. The euglycemic glucose clamp will be conducted using a manual clamp technique,

---

which will continuously monitor the participant's blood glucose and administer GIR to maintain blood glucose close to the target blood glucose concentration. The clamp procedure will be initiated, maintained, and terminated, in accordance with the site SOPs. The participant's blood glucose will be maintained within a predefined target window per site SOP and clinical judgement for the participant by manually adjusting the GIR.

The Target Glucose Value (TGV) for each participant is derived as follows (as described in the FAMOVS Standard Operating Procedure *Glucose Clamp Methodology CL14-v06 29-Jul-2024*):

The TGV is derived as the mean baseline glucose value (mg/dL) subtracted by 5 mg/dL. The mean baseline glucose value will be derived as the mean (rounded to the whole number) of the glucose values obtained at the -60, -30 and 0 time points.

The upper limit of the TGV is the mean baseline glucose value, and the lower limit value is the derived TGV subtracted by 5. As far as possible, the post dose glucose values of participants should be maintained within the upper and lower limit values by adjusting the GIR accordingly.

Blood samples will be collected at pre-specified intervals before and up to 12 hours after dosing for measurement of blood glucose, serum insulin, and C-peptide as shown in the schedule of assessments.

High glucose clamp quality is important to precisely and reproducibly describe the time-action profiles of blood glucose (BG) lowering agents. To achieve high quality, that is, a GIR reflecting the correct PD effect, BG must be kept at the TGV as closely as possible.

Calculations of the mean values, root mean square deviation and CV of the BG concentrations will be used to provide an estimate of the performance of the clamp study. The mean  $\pm$  SD difference between the clamp device and the target level reflects the "control deviation" and will be displayed in a figure. In this trial, the blood glucose CV% will be considered as a guide of good clamp technique. A blood glucose CV% below 10% has been suggested as the cut-off of sufficient clamp technique, i.e., CV %  $>$  10% is considered poor clamp technique.

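### Baseline is not defined by period: Period 2 and 3 vital-sign changes refer back to a value before the Period 1 dose, and onset of action does not say which baseline it uses

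*SAP*

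**What the plan says.** **General rule.** SAP 6.2, as a default that holds where no other rule is given: "baseline is defined as the last non-missing observation made prior to the first administration of IP". SAP 6.4 repeats this for change from baseline in quantitative measurements, "where the baseline value is defined as the last non-missing observation taken prior to first exposure to IP". In SAP 6.1 the reference start date is "defined as the date of first IP administration". Table 6.1 counts later visits from that date, putting the Period 2 clamp on Day 6–17 and the Period 3 clamp on Day 13–40.

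**Vital signs.** SAP 20.1: "For vital signs, baseline is defined as the last observation made prior to the first administration of IP". SAP 20.2 asks for actual values and change from baseline by visit, for each treatment sequence. The clamp columns of Protocol Table 3 cover Treatment Periods 1–3. Besides the screening and EOS visits, its footnote 9 times blood pressure, pulse and respiratory rate "before administration of the study drug, at the end of the clamp (before discharge from the study center"); body temperature is also taken before dosing.

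**Onset and duration of action.** SAP 23.2: "Time from study drug administration until the blood glucose concentration has decreased by at least 5mg/dL from baseline (onset of action"). Duration is tGIR,50%-late minus onset. Neither 23.2 nor the endpoint list in SAP 3.2 says which baseline is meant. SAP 24 describes a mean of the −60, −30 and 0 min glucose values and uses it for the clamp target: "The TGV is derived as the mean baseline glucose value (mg/dL) subtracted by 5 mg/dL". The upper limit of the band is that mean; the lower limit is the target minus a further 5 mg/dL.

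**The concern.** One baseline before the first dose suits a parallel-group trial. In a crossover every participant has three first exposures, one per product, each with its own pre-dose measurements. Tying Periods 2 and 3 to a value before the Period 1 dose discards the same-day reference and puts between-day drift into each change.

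For vital signs this is what the SAP says. For onset of action it is what the default gives if nothing overrides it, and 23.2 contains no override. At stake are the by-visit vital-sign changes and two named secondary PD endpoints, onset and duration. If the text is left as it is, a programmer must choose the glucose baseline, and that choice can move both endpoints.

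**Working it through.** **1. Age of the Period 1 baseline.** Inputs: SAP 6.1 (visit day = date − reference start date + 1), post-clamp on Day 2, and washouts of 3–14 and 5–21 days.
- Period 2 clamp: 2 + 3 + 1 = 6 to 2 + 14 + 1 = 17; post-clamp Day 7–18.
- Period 3 clamp: 7 + 5 + 1 = 13 to 18 + 21 + 1 = 40.

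This reproduces Table 6.1 exactly, so the first dose is a once-per-study event on Period 1, Day 1. A baseline taken that day is 6 − 1 = 5 to 17 − 1 = 16 days old at the Period 2 clamp, and 13 − 1 = 12 to 40 − 1 = 39 days old at the Period 3 clamp.

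**2. Vital signs.** Write Y_k for a post-dose value in Period k and B_k for the pre-dose value in that period. The SAP's change is

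Y_k − B_1 = (Y_k − B_k) + (B_k − B_1).

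The first term is the within-period change; the second is drift between visits. Footnote 9 schedules B_k, so the first term is available without new data. The documents give no between-day variance for vital signs, so the drift cannot be sized here.

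**3. Which baseline applies to onset?**
- SAP 6.2 default: one value, the last before the first dose.
- SAP 24: a rounded mean of three pre-dose values, introduced to set the clamp target, derived for each participant, with no statement that it is recomputed in each period.
- SAP 23.2 points to neither. SAP 10 sends secondary PD endpoints to Section 23, and SAP 11 sends exploratory endpoints to Section 24, so no cross-reference links onset to the Section 24 mean.

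The two definitions differ in kind, so they can give different onset times even in Period 1.

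**4. Literal default against the clamp band.** Let M_k be the Section 24 mean in Period k, taken as recomputed each period.
- Band: target M_k − 5; lower limit (M_k − 5) − 5 = M_k − 10; upper limit M_k.
- Literal onset threshold in every period: B_1 − 5.
- Already passed at dosing (onset = 0) if that day's fasting glucose ≤ B_1 − 5.
- At or below the lower limit if B_1 − 5 ≤ M_k − 10, that is M_k − B_1 ≥ 5.

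**5. How often.** Assume fasting values on two days are independent and normal with the same mean and within-participant between-day SD s. The documents do not give s. The same s is used for single readings and for the three-value mean, as a simplification. The difference has SD s√2, and each event has probability Φ(−5 / (s√2)).

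| Assumed s (mg/dL) | Onset = 0 | Threshold at or below lower limit |
|---|---|---|
| 2 | 3.9% | 3.9% |
| 3 | 11.9% | 11.9% |
| 4 | 18.8% | 18.8% |
| 5 | 24.0% | 24.0% |
| 6 | 27.8% | 27.8% |

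Of 54 × 3 = 162 planned clamps, 54 × 2 = 108 are in Periods 2 and 3. Each column is therefore about 0.039 × 108 ≈ 4 to 0.278 × 108 ≈ 30 clamps, before dropout. The other later-period thresholds are shifted by B_1 minus that day's baseline.

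**6. Bias or noise?** With six sequences allocated equally, each product is given in each period to 2/6 of participants, 18 of 54. Each product thus has 36 of its 54 planned clamps in Periods 2 and 3. The error depends on day-to-day glucose, not on product, so it falls on the three products alike apart from chance and dropout.

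**The case against.** SAP 6.2 is only a default, as its opening words show, and SAP 24 supplies a glucose baseline from pre-dose samples of the clamp. The target lies 5 mg/dL below that mean and onset is a fall of 5 mg/dL, which suggests that onset was meant as reaching the day's target. SAP 6.4 concerns differences between visits, not a time derived within one clamp. This stands as the sensible reading, and it limits the finding on onset to missing specification. It does not remove the gap, because the SAP never writes that reading down.

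On vital signs, the tables are descriptive, show actual values and are split by sequence; Protocol 14.5 itself uses change from screening, also a study-level reference. That limits the consequence. The text of 20.1 remains, and same-day values are available.

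Four stronger readings are tempting and are not supported:
- A reader might infer that two of the three products in every participant get a wrong onset. That holds only under the literal default, which the documents do not show will be used.
- A reader might add the two columns above (about 8% at s = 2 to 56% at s = 6) and call all those clamps invalid. That treats the lower limit as a hard floor; SAP 24 asks only that glucose be held within the limits as far as possible, so a lower threshold may still be crossed.
- A reader might conclude that the secondary PD objective cannot be answered. Six of the eight secondary PD endpoints in SAP 3.2 use no glucose baseline: the three partial AUCGIR values, Tmax.GIR and the two half-maximum times.
- A reader might extend the point to C-peptide. The SAP plans corrected and uncorrected concentrations, with no change from baseline.

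**Conclusion.** The point holds in two parts of different strength.

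**Vital signs: established on the text.** Period 2 and 3 changes are measured from a value 5–16 and 12–39 days old and mix drift with the product effect. The size is unknown, and no inferential test depends on it.

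**Onset and duration: an unresolved definition.** The literal default is a single Period 1 glucose value and conflicts with a band built from the clamp day's mean; the sensible alternative is not stated. If the default were applied, about 4–28% of Period 2 and 3 clamps would have onset at time zero, and a similar share would have a threshold at or below the lower limit. These figures rest on the assumed SD of 2–6 mg/dL, normality, a common mean across days and a band reset each period. The effect would be mainly extra noise and missing values, not bias between products.

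The four primary endpoints have no stated baseline term, so the equivalence tests and the sample size are untouched. The correction should be made before the analysis, because it concerns secondary and safety results and is easy to settle.

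**What to change.** - **SAP 6.2, 6.4 and 20.1:** for vital signs, define baseline as the last pre-dose value in the same period.
- **SAP 23.2:** state that onset of action, and so duration, uses the mean of that period's −60, −30 and 0 min glucose values, computed separately in each period by the Section 24 formula, and add the cross-reference.
- **Laboratory tests and ECG:** keep the baseline before the first dose, since Table 3 does not repeat these before each dose.
- **C-peptide:** no baseline is needed.

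The cost is SAP wording and the matching derivation code. The period-specific pre-dose measurements are already planned, and the clamp procedure is not changed. Settling the wording before unblinding avoids a post hoc choice of baseline.
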